
 To evaluate the efficacy of cobimetinib plus atezolizumab compared with pembrolizumab, as measured by OS and 2-year landmark OS To evaluate the efficacy of cobimetinib plus atezolizumab compared with pembrolizumab, as measured by ORR To evaluate the efficacy of cobimetinib plus atezolizumab compared with pembrolizumab, as measured by investigator-assessed PFS To evaluate the efficacy of cobimetinib plus atezolizumab compared with pembrolizumab, as measured by DCR To evaluate the efficacy of cobimetinib plus atezolizumab compared with pembrolizumab, as measured by DOR To evaluate the efficacy of cobimetinib plus atezolizumab compared with pembrolizumab, as measured by the change from baseline in HRQoL 	
 OS, defined as the time from randomization to death from any cause Two-year landmark survival, defined as survival at 2 years Objective response, defined as a complete response or partial response on two consecutive occasions ≥ 4 weeks apart, as determined by an IRC according to RECIST v1.1 Objective response, defined as a complete response or a partial response on two consecutive occasions ≥ 4 weeks apart, as determined by the investigator through use of RECIST v1.1 PFS, defined as the time from randomization to the first occurrence of disease progression, as determined by the investigator through use of RECIST v1.1, or death from any cause, whichever occurs first DCR, defined as the proportion of patients with a complete response, a partial response, or stable disease at 16 weeks, as determined by the IRC through use of RECIST v1.1 DCR, defined as the proportion of patients with a complete response, a partial response, or stable disease at 16 weeks, as determined by the investigator through use of RECIST v1.1 Duration of objective response, defined as the time from the first occurrence of a documented objective response to disease progression, as determined by an IRC according to RECIST v1.1, or death from any cause Duration of objective response, defined as the time from the first occurrence of a documented objective response to disease progression, as determined by the investigator through use of RECIST v1.1, or death from any cause, whichever occurs first The change from baseline in HRQoL scores, as assessed through use of the two-item GHS/QoL subscale of the EORTC QLQ-C30, at specified timepoints while receiving treatment

Table 1 Objectives and Corresponding Endpoints (cont.)

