4.2 METHOD OF TREATMENT ASSIGNMENT

This is an open-label trial. After written informed consent has been obtained and eligibility has been established, each patient will be assigned an identification number and be randomized to one of the two treatment arms through use of an IWRS.

Randomization will be stratified by PD-L1 status (IC0 vs. IC1, 2, 3), baseline LDH (less than or equal to the ULN vs. greater than the ULN), and geographic region (North America vs. Europe vs. Australia, New Zealand, and others). A stratified, permuted block randomization scheme will be used to obtain approximately a 1:1 ratio between the two treatment arms.

Patients should receive their first dose of study treatment as soon as possible and within 3 days of randomization, unless approved by Medical Monitor.

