4.5.11 Patient-Reported Outcomes

To more fully characterize disease burden and clinical benefit of atezolizumab and cobimetinib in patients with advanced melanoma, patient-reported outcome (PRO) data will be obtained through use of the following instruments: EORTC QLQ-C30 and the EQ-5D-5L. The questionnaires will be translated as appropriate into the local language. Reminders will be provided in order to maximize compliance. It is critical to rigorously collect the PRO data as they support the secondary and exploratory efficacy endpoints.

The EORTC QLQ-C30 and EQ-5D-5L will be completed on Day 1 of Cycle 1 and every 4 weeks thereafter, including prior to tumor assessments visits every 8 weeks. In addition, the questionnaires will be completed at the site for the treatment discontinuation visit and at unscheduled visits. All PRO questionnaires must be completed prior to any study assessment(s) that could bias a patient's responses.

Also, the PROs will be collected every 4 weeks for 6 months after the treatment discontinuation visit. PRO data collected post-study treatment will be used as a unique opportunity to quantify patients' post-treatment experience in terms of humanistic outcomes.

Patients will use an electronic device to capture all PRO data. Instructions to use the device and to complete the PRO questionnaires will be provided by site staff once the patient is randomized and before initiation of study treatment. The data will be transmitted to a centralized database maintained by the vendor and will be made available for access by appropriate study personnel at the site. In the event that the device or the Web-based system is not readily available, paper questionnaires formatted for use as backup data collection forms should be used to minimize missing data. Compliance with data collection will be documented throughout the study.

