7.3 ELECTRONIC PATIENT-REPORTED OUTCOME DATA

Upon randomization, patients will use an electronic device to capture PRO data. The device is designed for entry of data in a way that is attributable, secure, and accurate, in compliance with U.S. FDA regulations for electronic records (21 CFR, Part 11). The data will be transmitted to a centralized database maintained by the electronic device vendor.

The electronic data will be available for view access only, via a secure method. Only identified and trained users may view the data, and their actions will become part of the audit trail. The Sponsor will have view access only. System backups for data stored by the Sponsor and records retention for the study data will be consistent with the Sponsor's standard procedures.

Once the study is complete, the data, audit trail, and trial and system documentation will be archived. The investigator will receive patient data for the site in both human- and machine-readable formats on an archival-quality compact disc that must be kept with the study records as source data.

Acknowledgement of receipt of the compact disc is required. In addition, the Sponsor will receive all data in a machine-readable format.

In case of electronic device failure or patient refusal to use the electronic device, a paper backup solution will be implemented.

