- ^a Perform screening tests within 35 days prior to treatment initiation (Day 1) unless the patient meets criteria specified in Section 4.5.1. Standard-of-care screening assessments may be performed concurrently with *BRAF*^{V600} mutation and PD-L1 testing. *BRAF*^{V600} status must be known prior to performing study-specific screening assessments. The 35-day window begins at the time of the first standard-of-care screening assessment or the first study-specific screening assessment after the *BRAF*^{V600} mutation test result is available, whichever is earlier. Results of standard-of-care tests or examinations performed prior to obtaining informed consent and within 35 days prior to treatment initiation (Day 1) may be used; such tests do not need to be repeated for screening. For a list of laboratory tests for which results must be obtained within 14 days prior to the first dose of study drug, see Section 4.1.1.2. Test results should be reviewed prior to administration of study drug. PD-L1 will be assessed by central laboratory and the result will be used for stratification and randomization only.
- ^b Patients who discontinue study drug will return to the clinic for a treatment discontinuation visit within 30 (+7) days. The visit at which response assessment shows progressive disease may be used as the study discontinuation visit.
- ^c Required follow-up information will be collected via telephone calls and/or clinic visits every 3 months until death, loss to follow-up, or study termination by the Sponsor.
- ^d Day 1 of Cycle 1 can occur up to 3 days after randomization.
- ^e Visit not specified by the protocol. Assessments (possibly including PK sample collection) should be performed as clinically indicated.
- ^f Informed consent must be documented before any study-specific screening procedure is performed and may be obtained up to 35 days before initiation of study treatment.
- ^g Vital signs include respiratory rate, pulse rate, and systolic and diastolic blood pressure while the patient is in a seated position, and temperature. Resting oxygen saturation will be measured during screening and subsequent visits. Record abnormalities observed at baseline on the General Medical History and Baseline Conditions eCRF. At subsequent visits, record new or worsened clinically significant abnormalities on the Adverse Event eCRF.

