Appendix 1 Schedule of Activities (cont.)

Table 2 Arm B: Pembrolizumab Schedule of Activities (21-Day Cycles) (cont.)

-
- ^a Perform screening tests within 35 days prior to treatment initiation (Day 1) unless a patient meets criteria specified in Section 4.5.1. Standard-of-care screening assessments may be performed concurrently with *BRAF*^{V600} mutation and PD-L1 testing. *BRAF*^{V600} status must be known prior to performing study-specific screening assessments. The 35-day window begins at the time of the first standard-of-care screening assessment or the first study-specific screening assessment after the *BRAF*^{V600} mutation test result is available, whichever is earlier. Results of standard-of-care tests or examinations performed prior to obtaining informed consent and within 35 days prior to treatment initiation (Day 1) may be used; such tests do not need to be repeated for screening. For a list of laboratory tests for which results must be obtained within 14 days prior to the first dose of study drug, see Section 4.1.1.2. Test results should be reviewed prior to administration of study drug. PD-L1 will be assessed by central laboratory and the result will be used for stratification and randomization only.
- ^b Patients who discontinue study drug will return to the clinic for a treatment discontinuation visit within 30 (+7) days. The visit at which response assessment shows progressive disease may be used as the study discontinuation visit.
- ^c Required follow-up information will be collected via telephone calls and/or clinic visits every 3 months until death, loss to follow-up, or study termination by the Sponsor.
- ^d Day 1 of Cycle 1 can occur 3 days after randomization.
- ^e Visit not specified by the protocol. Assessments (possibly including PK sample collection) should be performed as clinically indicated.
- ^f Informed consent must be documented before any study-specific screening procedure is performed and may be obtained up to 35 days before initiation of study treatment.
- ^g Vital signs include respiratory rate, pulse rate, and systolic and diastolic blood pressure while the patient is in a seated position, and temperature. Resting oxygen saturation will be measured during screening and subsequent visits. Record abnormalities observed at baseline on the General Medical History and Baseline Conditions eCRF. At subsequent visits, record new or worsened clinically significant abnormalities on the Adverse Event eCRF.

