4.4.2.6 Patient-Reported Outcomes

The data from the PRO-evaluable population, which includes all randomized patients who have a baseline and at least 1 post-baseline assessment, will be used to assess change from baseline in global health status/HRQoL (items 29 and 30 of the EORTC QLQ-C30.) Visit summary and change from baseline analyses will be performed for the EORTC QLQ-C30 GHS/HRQoL scale scores. Summary statistics (number of patients, mean, SD, median, minimum, maximum) of score(s) will be presented by treatment arm and longitudinal score change(s) from baseline to each time point while patients are receiving treatment will inform statistical differences between treatment arm (see section [4.4.3.2.4](#)).

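### No QLQ-C30 is scheduled before open-label randomisation, so the baseline for the secondary global health change score can be influenced by knowledge of the arm

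*Protocol*

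**What the plan says.** Protocol 4.2 states: "This is an open-label trial". The first dose is to follow randomisation within 3 days unless the Medical Monitor agrees otherwise. Appendix 1 says for Arm A: "Day 1 of Cycle 1 can occur up to 3 days after randomization". The Arm B footnote reads "Day 1 of Cycle 1 can occur 3 days after randomization".

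On the questionnaires, Protocol 4.5.11 says "The EORTC QLQ-C30 and EQ-5D-5L will be completed on Day 1 of Cycle 1 and every 4 weeks thereafter". It adds that instructions for the device and the forms are "provided by site staff once the patient is randomized and before initiation of study treatment". Protocol 7.3 says "Upon randomization, patients will use an electronic device to capture PRO data". In both arms' schedules (Appendix 1, Tables 1 and 2) the questionnaire row is empty at screening, and its first mark is Cycle 1 Day 1.

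Protocol Section 2 lists as a secondary efficacy endpoint "The change from baseline in HRQoL scores, as assessed through use of the two-item GHS/QoL subscale of the EORTC QLQ-C30". SAP 4.4.2.6 uses the PRO-evaluable population, "which includes all randomized patients who have a baseline and at least 1 post-baseline assessment", and looks to longitudinal change from baseline for statistical differences between arms. Protocol 6.4.3 and SAP 4.4.3.2.3 also classify patients by a 10-point change from the same baseline.

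**The concern.** A baseline should be a value that treatment assignment cannot have touched. Here it is collected after assignment in an unblinded trial. A patient who hoped for the new combination and drew the standard drug, or the reverse, may rate overall health and quality of life differently for a few days. If that reaction differs by arm and then fades, subtracting the Day 1 score creates a between-arm difference in change with no drug effect behind it.

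Protocol 3.3.8 defends the open-label design by pointing to blinded independent review of PFS, response and duration, and to OS. It names no safeguard for HRQoL. At stake are the secondary global health comparison and the improved/stable/worsened proportions.

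**Working it through.** **Timing.** Five items together establish the point; the sentence on instructions would not do so alone.

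1. The first form is due on Cycle 1 Day 1 (Protocol 4.5.11; both schedules' questionnaire footnotes).
2. No form is marked at screening (Appendix 1, Tables 1 and 2).
3. Day 1 falls up to 3 days after randomisation (Protocol 4.2; Appendix 1).
4. Instruction and electronic capture both begin after randomisation (Protocol 4.5.11 and 7.3).
5. The trial is open-label, and no passage requires the form to be completed before the arm is known.

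**Size.** The plan gives no SD, power or sample size for HRQoL, so there is no stated figure to reproduce. What follows is illustrative. The only input from the documents is 225 randomised per arm. The assumed inputs are a baseline shift d of 2 to 5 points in one arm that is gone by follow-up, no true effect, SD of change 20–25, and 150–225 evaluable patients per arm.

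Raw change score: SE = SD × √(2/n), b = d/SE, and the rejection probability is Φ(−1.96 + b) + Φ(−1.96 − b).

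- n = 200, SD 20: SE = 20 × √(2/200) = 2.00. For d = 2, b = 1.00 and rejection is 17.0%. For d = 5, b = 2.50 and rejection is 70.5%.
- n = 150, SD 25: SE = 25 × √(2/150) = 2.89. For d = 2, b = 0.69 and rejection is 10.7%. For d = 5, b = 1.73 and rejection is 41.0%.

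Baseline-adjusted analysis at an assumed correlation ρ = 0.5: the bias is ρd = 0.5d. At ρ = 0.5 the SD of change equals the SD of a single score, so the residual SD is SD × √0.75. The two analyses compare as follows at 180–225 per arm, with SD 20–25:

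| Shift | Raw change score | Baseline-adjusted |
|---|---|---|
| 2 points | 12–19% | 7–9% |
| 3 points | 21–36% | 10–15% |
| 5 points | 48–76% | 20–33% |

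A 5-point shift is half of the 10-point change that Protocol 4.5.11.1 treats as clinically meaningful.

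**Which analysis applies.** The mixed model in Protocol 6.4.3 names baseline domain score as a covariate. The terms in SAP 4.4.3.2.4 are offered as ones the model may include, and baseline score is not among them. SAP Section 4 says the SAP supersedes the protocol for filing. Adjustment is therefore neither assured nor excluded.

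**The case against.** Several stronger readings are tempting, and the documents do not support them.

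- **That Section 4.5.11 breaks its own rule.** The rule puts questionnaires ahead of study assessments that could bias answers. Allocation is not a study assessment, so there is no internal contradiction.
- **That every patient knows the arm when answering.** No passage says when the patient is told, and Day 1 may be the day of randomisation. Knowledge of the arm is an inference from the open-label design.
- **That the upper false-positive figures describe this trial.** They rest on assumed inputs and an unadjusted change score. The one-week recall period (Protocol 4.5.11.1; Appendix 8) would also dampen a shift, since under the standard window at most about 3 of those 7 days follow allocation.
- **That an earlier baseline would free the PRO population from post-randomisation selection.** It would not: a post-baseline form is still required.

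The most serious counter-argument is that moving the baseline trades one bias for another. Suppose a fraction f of the shift d persists to follow-up. The raw-change bias is (f − 1)d with the Day 1 baseline and fd with a pre-randomisation one. Full persistence cancels under the current plan and remains under the alternative. That arithmetic is right, and no document says which case is likelier.

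It does not rescue the Day 1 baseline. A pre-randomisation score cannot differ systematically by arm. With a Day 1 reference, the contrast depends on how long an unmeasured reaction lasts. A lasting reaction affects the later open-label answers themselves, whichever baseline is used, and it cancels only if it persists exactly.

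Two further limits stand. HRQoL is absent from the hierarchy in SAP 2.3 (PFS, then OS, IRC-assessed ORR and landmark OS), so no alpha-controlled claim is exposed. SAP 2.5 records that the trial is ending early, so patients already randomised cannot be given an earlier baseline.

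**Conclusion.** The point holds as a design weakness. The reference value for a named secondary between-arm endpoint is collected after open-label allocation, with no earlier score to fall back on, and knowledge of the arm can influence it. Whether it did, in which direction and by how much cannot be told from the documents.

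The illustrative range is about 11–70% false positives for a 2–5 point transient shift on a raw change score (150–200 per arm). With baseline adjustment it is about 7–33% (correlation 0.5, 180–225 per arm). With no shift, or one that persists unchanged, the Day 1 baseline adds no such bias to the change score. PFS and OS are unaffected. This merits correction because the remedy is cheap, but it does not threaten the trial's main conclusions.

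**What to change.** In Protocol 4.5.11, Protocol 7.3 and both Appendix 1 schedules, have the baseline QLQ-C30 and EQ-5D-5L completed once eligibility is confirmed and before the IWRS allocation is requested, on the device or the existing paper backup. Define that form as the PRO baseline in SAP 4.4.2.6 and 4.4.3.2. If the Cycle 1 Day 1 form is kept, treat it as post-baseline; comparing the two would then show any early shift by arm.

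The cost is small. The forms take about 13 minutes (10 + 3, Protocol 4.5.11.1 and 4.5.11.2), and a few patients who are not then randomised will complete them. No new instrument or visit is needed, and sample size, events and power are unchanged. The change protects the reference value only; later questionnaires remain open-label.

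For patients already randomised, report baseline global health score by arm and baseline-form completion by arm among all randomised patients, include baseline score in the SAP 4.4.3.2.4 model, and state the limitation alongside the HRQoL results.

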4.5.11.1 EORTC QLQ-C30

The EORTC QLQ-C30 is a validated, reliable self-reported measure (Aaronson et al. 1993; Fitzsimmons et al. 1999) that is commonly used in clinical trials involving patients with metastatic melanoma (Revicki et al. 2012; Schadendorf et al. 2015). It consists of 30 questions that assess five aspects of patient functioning (physical, emotional, role, cognitive, and social), three symptom scales (fatigue, nausea and vomiting, pain), GHS/QoL, and six single items (dyspnea, insomnia, appetite loss, constipation, diarrhea, and financial difficulties) with a recall period of the previous week. Scale scores can be obtained for the multi-item scales. The EORTC QLQ-C30 module takes approximately 10 minutes to complete. A 10-point change is defined as a clinically meaningful difference for the EORTC QLQ-C30 (Osoba et al. 1998) and has been used in other melanoma studies (Long et al. 2016; Shadendorf et al. 2015).

4.5.11.2 EQ-5D-5L

The EQ-5D-5L is a validated, self-reported health status questionnaire that is used to calculate a health status utility score for use in health economic analyses (EuroQol Group 1990; Brooks 1996; Herdman et al. 2011; Janssen et al. 2013). There are two components to the EQ-5D-5L: a five-item health state profile that assesses mobility, self-care, usual activities, pain/discomfort, and anxiety/depression, as well as a visual analog scale that measures health state. Published weighting systems allow for creation of a single composite score of a patient's health status. The EQ-5D-5L takes approximately 3 minutes to complete. It will be utilized in this study for informing pharmacoeconomic evaluations.

4.6 TREATMENT, PATIENT, STUDY, AND SITE DISCONTINUATION

4.6.1 Patient Discontinuation from Study

Patients have the right to voluntarily withdraw from the study at any time for any reason. In addition, the investigator has the right to withdraw a patient from the study at any time. Reasons for withdrawal from the study may include, but are not limited to, the following:

- Patient withdrawal of consent at any time
- Study termination or site closure
- Any medical condition that the investigator or Sponsor determines may jeopardize the patient's safety if he or she continues in the study
- Investigator or Sponsor determines it is in the best interest of the patient
- Patient non-compliance

Every effort should be made to obtain information on patients who withdraw from the study. The primary reason for withdrawal from the study should be documented on the appropriate eCRF. However, patients will not be followed for any reason after consent has been withdrawn. Patients who withdraw from the study will not be replaced.

If a patient withdraws from the study, the study staff may use a public information source (e.g., county records) to obtain information about survival status.

4.6.2 Study Treatment Discontinuation

Patients must permanently discontinue study treatment if they experience any of the following:

- Confirmed disease progression or loss of clinical benefit (see Section 3.1.2 for dosing beyond progression)
- Symptomatic deterioration attributed to disease progression, as determined by the investigator, after integrated assessment of radiographic data, biopsy results, and clinical status
- Intolerable toxicity related to any study drug
- Any medical condition that the investigator or Sponsor determines may jeopardize the patient's safety if he or she continues to receive study treatment
- Use of another non-protocol-specified anti-cancer therapy (see Section 4.4.2)
- Pregnancy
- Withdrawal of consent
- Investigator or Sponsor determines it is in the best interest of the patient (e.g., unwillingness to comply with study assessments that compromise their safety)
- Any adverse event that requires study treatment discontinuation per the guidelines in Section 5.1, Appendix 10, and Appendix 11.

- In cases where discontinuation of one study drug is required for toxicity, patients may continue on the remaining drug (Arm A only) per the guidelines in Section 5.1 and Appendix 10.

The primary reason for study drug discontinuation should be documented on the appropriate eCRF. Patients who discontinue study treatment will not be replaced.

